14.5 Physical Examinations

Clinically significant abnormalities observed during physical examinations will be summarized by visit and presented in listings.

Body weight, height and body mass index (BMI) will be summarized by visit.

14.6 Pregnancy Test

At Screening and at any time during the study, a female subject judged by the investigator to be of childbearing potential (as defined by onset of menses) will be tested for pregnancy with a urine pregnancy test; additional urine tests will be performed whenever pregnancy is in question. A serum pregnancy test will be performed if a urine test result is positive or equivocal.

The test results will be provided in a listing.

14.7 Neurological Examination

A complete neurological examination includes level of consciousness, speech, language, cranial nerves, motor strength, motor tone, abnormal movements, reflexes, upper extremity sensation, lower extremity sensation, gait, Romberg, nystagmus, and coordination.

The neurological examination results (normal vs abnormal) will be listed only.

14.8 Cerebrospinal Fluid Surveillance (CSF)

Samples of standard clinical laboratory CSF for routine surveillance (cell count with differential, protein, glucose, and culture) will be summarized in a similar manner to clinical lab tests.

	BMN 190-203 Statistical Analysis Plan, Version 2.0	Pg. 43 of 53
---	---	--------------

15 IMMUNOGENICITY ASSESSMENT

Immunogenicity tests will be performed using validated immunogenicity assays. Routine immunogenicity tests will include total antibody (TAb) and neutralizing antibody (NAb) in the serum and CSF. NAb testing will not be performed if the TAb is negative. Incidence and titer summary statistics will be provided for serum TAb, CSF TAb, serum NAb, and CSF NAb in table format and will include mean, median, standard deviation, and minimum/maximum titer values at each study visit. Immunogenicity will be summarized by visit as well as by change at study timepoint from baseline. Potential impact of anti-drug antibodies (ADA) on efficacy and safety will be explored.

In the event of serious or severe (\geq Grade 3) hypersensitivity AE, a blood sample will be collected no sooner than 8 hours after the event (or before the next infusion) for drug-specific IgE testing. Potential associations between immunogenicity results and hypersensitivity adverse events might be analyzed.

	BMN 190-203 Statistical Analysis Plan, Version 2.0	Pg. 44 of 53
---	---	--------------

16 PHARMACOKINETICS AND PHARMACODYNAMICS

The analysis of pharmacokinetics (PK) and pharmacodynamics (PD) will be finalized prior to final database lock as a separate document.

Draft

BIOMARIN®	BMN 190-203 Statistical Analysis Plan, Version 2.0	Pg. 45 of 53
------------------	---	--------------

17 APPENDICES

Appendix 1: Windows

Assessment	Derived Visit	Scheduled Visit Day	Window (day)
Device patency/infection, Brief physical examination i=1,2,...71	Baseline	1	<=1
	Day 6	6	[2, 10]
	Week 3	15	[11, 22]
	Week 3 + i*2	15 + i*14	[9+i*14, 22+i*14]
CSF (cell count, protein, glucose, and culture). i=1,2,...70	Baseline	1	<=1
	Day 6	6	[2, 10]
	Week 3	15	[11, 22]
	Week 3 + i*2	15 + i*14	[9+i*14, 22+i*14]
	Week 145	1016	Day 1003 and later
Vital Signs i=1,2,...70	Baseline	1	Pre-dose
	Day 1	1	Post-dose
	Week 3	15	[2, 22]
	Week 3 + i*2	15 + i*14	[9+i*14, 22+i*14]
	Week 145	1016	[1003, 1092]
	Week 169		Day 1093 and later
CLN2 disease rating scale* i=1,2,...34	Screening		Screening visit
	Baseline	<1	<=1
	Week 5	29	[2, 43]
	Week 5 + i*4	29 + i*28	[16+i*28, 43+i*28]
	Week 145	1016	[996, 1092]
	Week 169		Day 1093 and later
Modified Unified Batten Disease Rating Scale Involuntary Movement Scale, Modified Unified Batten Disease Rating Scale Seizure Inventory i=1,2,...11	Baseline	<1	<=1
	Week 13	85	[2, 127]
	Week 13 + i*12	85 + i*84	[44+i*84, 127+i*84]
PedsQL, Denver II Developmental Scale.	Baseline	<1	<=1
	Week 13	85	[2, 127]

BIOMARIN®	BMN 190-203 Statistical Analysis Plan, Version 2.0	Pg. 46 of 53
------------------	---	--------------

CLN2-specific QoL questionnaire, Visual acuity testing, Neurological examination CSF for immunogenicity ITQOL 4Q-5D-5L i=1,2,...10	Week 13 + i*12	85 + i*84	[44+i*84, 127+i*84]
	Week 145	1016	Day 968 and later
Serum for immunogenicity i=1,2,...10	Baseline	<1	<=1
	Week 13	85	[2, 127]
	Week 13 + i*12	85 + i*84	[44+i*84, 127+i*84]
	Week 145	1016	[968, 1092]
	Week 169		Day 1093 and later
ECG, 3- or 5-lead	Baseline	1	Pre-dose
	Day 1	1	Post-dose
ECG, 12-lead** i=1,2,...4	Baseline	<1	<1
	Day 1 - 30 minutes	1	1
	Week 25	169	[2, 253]
	Week 25 + i*24	169 + i*168	[86+i*168, 253+i*168]
	Week 145	1016	[926, 1092]
	Week 169		Day 1093 and later
Cranial MRI i=1,2,3,4	Screening		Screening visit
	Baseline	<1	<=1
	Week 25	169	[2, 253]
	Week 25 + i*24	169 + i*168	[86+i*168, 253+i*168]
	Week 145	1016	Day 926 and later
CSF / plasma for PK	Baseline	1	Pre-dose
	Day 1	1	Post-dose
	Week 25	169	[2, 253]
	Week 49	337	[254, 505]
	Week 97	673	Day 506 and later
CSF for disease-related biomarkers	Baseline	1	<=1

BMN 190-203 Statistical Analysis Plan, Version 2.0

Pg. 47 of 53

i=1,2..33 j=1,2,..8	Week 3	15	[2, 22]
	Week 3 + i*2	15 + i*14	[9+i*14, 22+i*14]
	Week 71	491	[485, 498]
	Week 79	547	[499, 575]
	Week 79 + j*8	15 + j*56	[520+j*56, 575+j*56]
	Week 151	1058	Day 1024 and later
Blood for disease-related biomarkers i=1,2,3,4 j=1,2,3,4,5,6	Baseline	1	Pre-dose
	Week 9	57	[1, 85]
	Week 9 + i*8	57 + i*56	[30+i*56, 85+i*56]
	Week 49	337	[310, 379]
	Week 61	421	[380, 463]
	Week 61 + j*12	421 + j*84	[380+j*84, 463+j*84]
	Week 145	1016	Day 968 and later
EEG, standard awake, Optical coherence tomography, i=1,2,3,4	Baseline	<1	<=1
	Week 25	169	[2, 253]
	Week 25 + i*24	169 + i*168	[86+i*168, 253+i*168]
	Week 145	1016	Day 926 and later
	Week 145	1016	Day 926 and later
Height and weight assessments i=1,2,..4	Baseline	<1	<=1
	Week 25	169	[2, 253]
	Week 25 + i*24	169 + i*168	[86+i*168, 253+i*168]
	Week 145	1016	[926, 1092]
	Week 169		Day 1093 and later
Ophthalmologic assessments	Baseline	1	<=1
	Week 49	337	[2, 505]
	Week 97	673	[506, 841]
	Week 145	1016	Day 842 and later
Complete physical examination	Baseline	1	<=1
	Week 49	337	[2, 505]
	Week 97	673	[506, 841]
	Week 145	1016	[842, 1092]

BMN 190-203 Statistical Analysis Plan, Version 2.0

Pg. 48 of 53

	Week 169		Day 1093 and later
Blood/urine for clinical lab tests i=1,2,3 j=1,2,3,...6	Baseline	<=1	<=1
	Day 2	2	2
	Week 5	29	[3, 43]
	Week 9	57	[44, 71]
	Week 17	113	[72, 141]
	Week 17 + i*8	113 + i*56	[86+i*56, 141+i*56]
	Week 49	337	[310, 379]
	Week 61	421	[380, 463]
	Week 61 + j*12	421 + j*84	[380+j*84, 463+j*84]
	Week 145	1016	[968, 1092]
	Week 169		Day 1093 and later

*: only motor, language and motor-language scores will be summarized for screening visit.

**: In patients with present or past bradycardia, conduction disorders, or with structural heart disease, ECG will be performed within 30 minutes before the start of infusion (± 5 minutes), at 2 hours (± 15 minutes) during infusion, 30 (± 5) minutes after infusion end, and 12 hours (± 3 hours) after infusion end. In this case, please use the prior infusion assessment on Day 1 as baseline.

6-month Safety follow-up (Week 169) is defined using the window week of 156 to infinite.

BIOMARIN®	BMN 190-203 Statistical Analysis Plan, Version 2.0	Pg. 49 of 53
------------------	---	--------------

Appendix 2: Estimation of Rate of decline for a Subject

The rate of decline on ML is based on selecting a starting and ending ML assessment. For Study 190-203 and Study 190-901, the starting assessment is the baseline ML assessment and the ending assessment is the last ML score > 0 . Note that for Study 190-901, the baseline ML assessment is defined as the assessment of matching to the Study 190-203 subject.

The rate of decline is calculated as follows:

1. Determine the slope of the line connecting the two points:

$$\text{Slope} = \frac{(\text{Ending ML score}) - (\text{Starting ML score})}{(\text{Ending date}) - (\text{Starting date})}$$

2. Calculate the rate of decline as the negative of the line's slope, scaled to a 48-week time period:

$$\text{Rate of decline} = (-1) \times (48 \times 7) \times \text{Slope}$$

Appendix 3: Matching of Study 190-901 and Study 190-203 Subjects

The population for the primary analysis is based on the ITT population and a 3-1 matching algorithm. This matching algorithm is based on maximizing the number of Study 190-203 subjects matched to Study 190-901 subjects and satisfying several criteria (baseline ML score equal, genome: equal number of common alleles, baseline age close and no more than 3 months apart). The data of Study 190-901 subjects will be restricted and includes the assessment at the age of the match as the baseline assessment. Duration of follow-up is measured with respect to this baseline. Follow-up assessments up to the largest duration that is less than or equal to the full follow-up duration of the matched 190-203 subject are included for the matched analysis. If this derived duration of follow-up for the Study 190-901 subject is not of duration 6 months or greater, then matching at this age of assessment will not be considered. For Study 190-901, where the first assessment of ML has the value 6, backwards imputation of the value 6 to earlier ages is allowed.

Distance is defined as the absolute value of the difference in baseline age for the potential match. Study 190-203 subjects are paired off from first through last and there are potentially 14 matched pairs. No Study 190-901 subject is matched more than once. To maximize the number of matched pairs, and overall low mean squared distance, at each pairing:

- Identify the Study 190-203 subject who has not yet been matched and has the least potential Study 190-901 candidates for pairing based on the requirement for equal baseline ML score, equal number of common alleles and distance ≤ 3 . If greater than one Study 190-203 subject is identified, break the tie by considering the number of potential Study 190-901 candidates for matching based on the requirement of distance ≤ 2 . Potentially, there are still ties and repeat as needed using distance criteria based on thresholds ≤ 1 and ≤ 0 .
- For the selected Study 190-203 subject, match with the Study 190-901 subject who has not yet been matched and has a (ML, age of assessment) combination that minimizes the distance measure. There may be greater than one Study 190-901 subject that satisfies minimal distance, in which case choose the 190-901 subject who has fewest potential Study 190-203 matches based on the distance ≤ 3 points (and ≤ 2 , ≤ 1 , ≤ 0 as needed). If there are no Study 190-901 subjects who satisfy distance ≤ 3 , then there is no match for the Study 190-203 subject.
- It is possible that there remains greater than one 901 patients selected. In this situation, ties are broken down based on the following criteria ordered: onset age, seizure age, exact genome, sex, country, most recent date of birth. For Study 203 patients missing onset (seizure) age, matching 901 patient(s) must have missing onset (seizure) age or onset (seizure) age after age of match.

	BMN 190-203 Statistical Analysis Plan, Version 2.0	Pg. 51 of 53
---	---	--------------

Repeat till all Study 190-203 subjects have been attempted for match. This completes a 1-1 matching. To attain 3-1 matching, cycle through the Study 190-203 subjects twice more. Study 190-203 subjects will have 3, 2, 1, or 0 Study 190-901 subjects matched. We refer to the group as a matched set. For analysis purposes, Study 190-203 subjects will have a weight of one and Study 190-901 subjects will be weighted inversely to the number of matches (1/3, 1/2, 1) and the weights will be normalized to the number of Study 190-901 subjects matched to Study 190-203 subjects.

Draft

BIOMARIN®	BMN 190-203 Statistical Analysis Plan, Version 2.0	Pg. 52 of 53
------------------	---	--------------

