13 EFFICACY EVALUATIONS

The efficacy analyses will be based on the ITT population. The PP population will be used for sensitivity analyses of the primary endpoint.

There will be two sets of efficacy analyses. The first set will be descriptive summaries of the Study 190-203 subjects at baseline and follow-up visits for all efficacy endpoints. The second set of analyses are for the CLN2 scales M, L, V, S, ML, MLV, and MLVS and based on matching Study 190-203 subjects to Study 190-901 historical controls. These will include descriptive summaries and statistical model results for treatment comparison to natural history. If natural history data are available on siblings with disease, data of sibling pairs will be presented in listings and graphical displays.

The primary efficacy endpoint is the rate of decline in the 0 to 6-point ML score and the primary analysis is based on matching with Study 190-901 subjects. All matched analyses will be based on a single matched set and the algorithm for matching has been prespecified prior to any matched analyses and is described in [Appendix 3](#). The matching will be a 3-1 matching of the Study 190-901 Evaluable population and the Study 190-203 ITT population. The matching criteria are:

- Equal ML score
- Age within 3 months
- Genome: equal number of common alleles (c.622C→T, c.509.1G→C)

For all matched analyses, Study 190-901 subjects will be weighted inversely to the number of Study 190-901 subjects matched to a given Study 190-203 subjects. The weights for 3, 2, and 1 Study 190-901 subject(s) matched to a given Study 190-203 subject will be 1/3, 1/2, and 1 respectively and the weights are normalized to the number of Study 190-901 subjects matched to Study 190-203 subjects.

To demonstrate comparability of the matched groups, summaries of the following variables will be produced for each group, with Study 190-901 subjects weighted according to number of matches.

- Age (years, continuous)
- Sex (Female/Male)
- Genome
- Site / Region
- M, L, ML, MLVS scale scores

	BMN 190-203 Statistical Analysis Plan, Version 2.0	Pg. 27 of 53
---	---	--------------

- Age of diagnosis (years)
- Age of first symptoms (years)

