13.1.2 Sensitivity Analysis Method(s)

The rate of ML decline endpoint will also be analyzed as follows:

- Repeat primary analysis (T-test) on the PP population by removing any matched set where the Study 190-203 member is not within the PP population.
- Test difference in rate of ML decline using the Sign test (Binomial) for the ITT and PP populations. The slope for each matched Study 190-203 patient is compared to the average slope of the Study 190-901 subject (s) of the 3-1 matched set.
- Repeat primary analysis on the baseline ML<6 population and baseline ML=6 population

	BMN 190-203 Statistical Analysis Plan, Version 2.0	Pg. 28 of 53
---	---	--------------

- If not all Study 190-203 subjects have at least one Study 190-901 match, produce summary statistics for the rate of ML decline for the ITT and matched Study 190-203 populations.
- Repeat primary analysis but without the use of weights (equal weighting)

Analyses of other measures of ML change are outlined in the next subsections and are based on the ITT population with matching.

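### Does carrying ML=6 back to younger ages in registry controls bias the matched comparison enough to change the plan?

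*SAP*

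**What the plan says.** SAP Section 13 matches up to three Study 190-901 children to each treated child on equal ML score, age within 3 months and number of common alleles. "All matched analyses will be based on a single matched set". For controls, Appendix 3 adds that "where the first assessment of ML has the value 6, backwards imputation of the value 6 to earlier ages is allowed", with no limit on how far back.

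The matched age becomes Day 1 and baseline (Sections 4.3 and 4.4). Follow-up, including the 6-month minimum, is counted from it. The Appendix 2 rate is a two-point slope from that baseline, where "the ending assessment is the last ML score > 0".

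The candidate chosen is one who "has a (ML, age of assessment) combination that minimizes the distance measure". If several are equally close, the rule is to "choose the 190-901 subject who has fewest potential Study 190-203 matches". Remaining ties go to onset age and then seizure age. When the treated child has no recorded onset (seizure) age, the control "must have missing onset (seizure) age or onset (seizure) age after age of match".

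Section 13.1.2 plans to "Repeat primary analysis on the baseline ML<6 population and baseline ML=6 population". No listed analysis is limited to observed baselines, and the comparability summary in Section 13 does not count imputed ones.

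**The concern.** The rule is one-sided. Two registry children may both have been at 6 at the match age, but only the one still at 6 when first scored can be used. Staying at 6 is part of the outcome, so imputed controls carry a stretch of guaranteed decline-free time that the slope then divides by. A copied 6 can also sit at age distance 0 and be preferred to an observed 6 that is one to three months away.

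Because there is one matched set, every planned analysis of the ML=6 children inherits this. The ML<6 repeat is free of it, since only the value 6 is carried back, but it does not cover the children concerned. At stake is the control rate in the ML=6 comparison and, through those sets, part of the primary analysis. How large a part cannot be stated, because the number of treated children with baseline ML=6 is not given.

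**Working it through.** The plan gives no figure to reproduce: there is no power calculation, and nothing on how many controls are imputed or over what interval. The check has four parts.

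**1. Mechanism.** Let a control have g weeks of imputed ML=6, then decline at 2.12 points per 48 weeks (the historical-control mean in Protocol 7.2), over T weeks in all.

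Rate = 48 × D / (g + t), where D = min(2.12 × (T − g)/48, 5) and t = min(T − g, 5 × 48/2.12 = 113.2). The cap of 5 keeps the last score above 0.

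| T | g = 0 | g = 24 | g = 48 |
|---|---|---|---|
| 144 weeks | 2.12 | 240/137.2 = 1.75 | 48 × 4.24/144 = 1.41 |
| 96 weeks | 2.12 | 48 × 3.18/96 = 1.59 | 48 × 2.12/96 = 1.06 |

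This shows the direction only. A child at 6 with an observed baseline also has decline-free time ahead, so the proper comparison is with all children at 6 at that age.

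**2. The rule in isolation.** Assumptions: ML decline starts at mean 36, SD 7 months (Protocol 7 puts symptom onset typically at ages 2 to 4); decline at 2.12 per 48 weeks; scores rounded to integers; match at 18 months; follow-up capped at 33 months, with at least 6 months required. The simulation used 400,000 trajectories per case. Rates are in points per 48 weeks.

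| Age at first registry score (assumed) | Visits | All children at 6 | Imputed controls |
|---|---|---|---|
| Within 12 months of onset | 6-monthly | 0.85 | 0.81 (5% low) |
| Within 12 months of onset | 12-monthly | 0.72 | 0.67 (about 7% low) |
| 6–36 months | 6-monthly | 0.85 | 0.78 (8% low) |
| 6–36 months | 12-monthly | 0.72 | 0.64 (11% low) |
| 24–60 months | 6-monthly | 0.85 | 0.64 (25% low) |
| 24–60 months | 12-monthly | 0.72 | 0.50 (31% low) |

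If entry is within 6 months of onset, the shortfall is 0.00–0.02. If children are scored from near birth there is no imputation and the effect is zero.

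**3. The rule inside the Appendix 3 algorithm.** Further assumptions: 3 or 7 treated children at ML=6, aged 12–36 months, with no recorded onset; allele classes 25/50/25%; a registry of 72, of whom 30 or none are scored 6-monthly from birth; 6-monthly visits. The true rate is about 1.2, and 44–95% of the ML=6 controls are imputed.

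| Age at first registry score | Net error, SAP tie-breaks | Net error, random tie-breaks |
|---|---|---|
| Symptom-driven | 0.00 to +0.07 | −0.07 to +0.02 |
| 6–36 months | −0.02 to +0.05 | −0.05 to −0.01 |
| 24–60 months | −0.17 to −0.06 (5–14% low) | −0.19 to −0.11 |

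So the tie-breaks offset the selection in the first two cases. If all 72 children are scored from birth, nothing is imputed and the tie-breaks alone give +0.03 to +0.09.

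**4. The alternative.** Restricting ML=6 controls to observed 6s within 3 months of the match age was tested on the part 2 assumptions with 6-monthly visits. With entry within 12 months of onset, these controls decline at 1.64 against 0.85 for all children at 6, because an observed 6 then lies close to onset. With entry at 6–36 months they give 0.87, close to the target. With entry at 24–60 months none exists, since the age window ends at 21 months. In the full algorithm with symptom-driven entry, the re-match overstates control decline by 0.06–0.16 if 30 children are scored from birth and by 0.44–0.60 if none are. Up to 46% of the treated children in those sets go unmatched.

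**The case for a change.** The best case for acting is that the selection is real and nothing planned exposes it. With wide visit spacing, a control's only follow-up score can be the very 6 that was carried back, giving a slope of exactly zero. For example, take a match at 12 months, a first score of 6 at 36 months, the next score at 48 months and a treated child followed for 144 weeks (about 33 months). The 6-month minimum does not catch this, because it too runs from the imputed baseline. The onset-age condition makes an imputed 6 plausible but is satisfied by exactly the children who decline late. A reader of the ML=6 result could not tell whether none or most of the controls are imputed.

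All of that stands as description. It does not establish a material net bias. The documents point to at least some early scoring: Protocol 11.1 describes half-yearly scores starting at birth for about 30 Hamburg children, and SAP Section 4.1.3 drops age-0 records, so such records exist. Neither gives proportions for the whole registry. Part 3 also treats every ML=6 child as having no recorded onset. Section 13.2.1 defines asymptomatic as MLVS 12, so a child at ML 6 may already have seizures, and the onset and seizure tie-breaks then match on those ages. The planned summary of age at first symptoms by matched group would show a control group with markedly late onset.

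The wish for a count of imputed controls is fair. It changes no estimate, and the analysts can add it to the comparability table without touching the plan.

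**Conclusion.** No change to the plan. Carrying a maximum score back in a progressive disease gives a plausible value, and it serves the stated aim of matching as many treated children as possible. Its isolated effect is neutral or slows the apparent control decline, which narrows the difference from the treated group; it is not a route to a false positive.

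Within the full matching procedure the net error is about nil or slightly the other way (−0.02 to +0.07 on a rate of about 1.2) for symptom-driven entry or entry at 6–36 months. It is 5–14% low only if first scores fall at 24–60 months. These sizes rest on assumed onset, entry and visit patterns; the true size cannot be found from the documents.

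The observed-baseline alternative is a trade-off, not a gain. It can err by more, and in the drug's favour; it can leave young children without a match, for whom Section 13.1.2 offers only "If not all Study 190-203 subjects have at least one Study 190-901 match, produce summary statistics"; and it has nothing to match on where the present rule is weakest. It would also be added after matched interim results had been produced (Section 3.6.1). What remains is a reporting courtesy: the number of imputed controls, the months to their first observed score, and how many have that 6 as their only follow-up score.

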Appendix 4: Imputation of CLN2 Scores at Nominal Time points

To enable a descriptive assessment of CLN2 scores at common time points in which all subjects contribute to the descriptive statistics, each subject of the 190-203 and 190-901 studies will have their CLN2 scores imputed to those time points.

Nominal time points are Weeks 4, 8, 12, ... 144, 168 with corresponding target Analysis Days 29, 57, 85, ... 1009, 1177.

The imputed CLN2 value at each target Analysis Day is calculated by linear interpolation. If a target Analysis Day is not bracketed on both sides by CLN2 scores, but there is a single CLN2 assessment within 28 days, inclusive, of the target Analysis Day, then that single assessment is used for imputation (observation carried forward). The imputed data of the 190-901 subjects is truncated to have no longer follow-up than the corresponding imputed data for the Study 190-203 subject matched.

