4.3 Study Day Derivation

A study day will be obtained by subtracting the initial study drug start date from a visit date plus 1 if the visit date occurs after the initial study drug start date. Otherwise, the study day will be the visit date minus the initial study drug start date. Therefore, Study Day 1 will be the same date as the initial study drug start date.

For Study 190-901, the time of events is presented in terms of the subjects' age, in units of months. The Study 190-901 assessment that is used as a match to a Study 190-203 subject will be assigned as Study Day 1. Study Day is assigned to subsequent records assuming 30-day months, e.g., Study Day 31, 61, 91, etc.

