4.5 Visit Windows for Analysis

Clinical variables assessed at scheduled visits will be summarized by visit. Assessments will be classified to visit windows centered on the target scheduled visit study day. If more than one assessment falls within a window, the closest assessment to the target is selected for analysis. If two assessments are equally closest to the target, then the later assessment is selected. Details for the visit windows definition are provided in [Appendix 1](#).

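### SAP Appendix 1 prints target days that contradict its own windows (Week 145 at Day 1016 instead of 1009, and two CSF biomarker targets), and the Section 4.3 formula gives Day 0 at first dose; the effect is confined to descriptive by-visit summaries

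*SAP*

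**What the plan says.** SAP Section 4.5 sets the selection rule. Each window is built around its target day: "Assessments will be classified to visit windows centered on the target scheduled visit study day". Where several records compete, nearness decides: "If more than one assessment falls within a window, the closest assessment to the target is selected for analysis". A tie goes to the later record. The targets and windows are in SAP Appendix 1.

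- **Week 145.** The CLN2 row reads "Week 145 1016 [996, 1092"]. The other rows that print a Week 145 day also give 1016. For two-weekly CSF surveillance the window is "Day 1003 and later"; for vital signs it is Days 1003 to 1092.
- **CSF biomarkers after Week 79.** The target is 15 + j×56 and the window is 520 + j×56 to 575 + j×56, for j = 1 to 8. The last line is "Week 151 1058 Day 1024 and later".
- **Appendix 4.** The nominal weeks 4, 8, 12, … 144, 168 have "corresponding target Analysis Days 29, 57, 85, ... 1009, 1177". This text is correct and serves as the comparator.
- **Section 4.3.** Study Day is the date difference "plus 1 if the visit date occurs after the initial study drug start date", and otherwise the plain difference. The section then concludes that the first-dose date is Day 1.

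**The concern.** Under a closest-to-target rule the target day decides which record is reported whenever a window holds more than one. The Week 145 windows are wide or open-ended, so a child who continues past Week 145 can have several two-weekly records in that window. A target seven days late moves the choice toward the later visit. The biomarker targets cannot be coded sensibly at all, because none lies inside its own window. The Study Day formula and its stated result cannot both be programmed.

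The same targets and the same Study Day wording appear in the June 2020 SAP, which was prepared for the interim report, so existing programs may already carry them.

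**Working it through.** **1. Week-to-day convention.** Appendix 4 follows day = 1 + 7w: Week 4 gives 29, Week 8 gives 57, Week 12 gives 85, Week 144 gives 1009 and Week 168 gives 1177. All are reproduced. Appendix 1 follows day = 1 + 7(W − 1). This reproduces Weeks 3, 5, 9, 13, 17, 25, 49, 61, 71, 79 and 97 (Days 15, 29, 57, 85, 113, 169, 337, 421, 491, 547, 673). Two fixed targets fail:

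- Week 145: 1 + 7×144 = 1009; printed 1016 = 1 + 7×145.
- Week 151: 1 + 7×150 = 1051; printed 1058 = 1 + 7×151.

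Both misprints equal what the Appendix 4 formula gives for an Appendix 1 week number.

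**2. What the rest of Appendix 1 implies for Week 145.** Two rows reach it by formula: device patency/brief physical examination at i = 71 (15 + 71×14 = 1009) and mUBDRS at i = 11 (85 + 11×84 = 1009). The printed lower bounds, with the target-to-lower-bound offset of the other visits in each row, agree:

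| Rows | Lower bound + offset | Target |
|---|---|---|
| CLN2 (four-weekly) | 996 + 13 | 1009 |
| CSF surveillance, vital signs (two-weekly) | 1003 + 6 | 1009 |
| 12-weekly | 968 + 41 | 1009 |
| 24-weekly | 926 + 83 | 1009 |
| 48-weekly | 842 + 167 | 1009 |

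The Week 169 window opens at Day 1093, which is the midpoint (1009 + 1177)/2.

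**3. CSF biomarkers.** The printed targets run from 15 + 56 = 71 to 15 + 8×56 = 463. The windows run from [576, 631] to [968, 1023]. Week 79 is Day 547, so Week 79 + 8j is 547 + j×56, or Days 603 to 995, each inside its window. The printed targets are 547 − 15 = 532 days early. The Week 151 bound is 1024 = 520 + 9×56, which goes with 547 + 9×56 = 1051.

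**4. Effect on selection at Week 145.** For two records on days x < y and target t, the later one is chosen when y − t ≤ t − x, that is, when x + y ≤ 2t. With t = 1009 the limit is 2018; with t = 1016 it is 2032. The choice changes when x + y is 2019 to 2032.

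- *Two-weekly visits* at 1009 + a and 1023 + b, with a and b from −3 to 3: the sum is 2032 + a + b. With t = 1016 the later visit is chosen when a + b ≤ 0, which is 7 + 21 = 28 of 49 pairs (57%). With t = 1009 it would need a + b ≤ −14, so 0 of 49. On schedule, Days 1009 and 1023 are each 7 days from 1016, and the tie rule takes 1023.
- *Four-weekly visits* at 1009 + a and 1037 + b: the sum is 2046 + a + b, so a change needs a + b ≤ −14. None of 49. Visits 84 days apart also give none.

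**5. Effect for biomarkers.** A target below the window always selects the earliest record: of Days 578 and 603 it takes 578, where the corrected target takes 603. On the protocol schedule, however, there is normally one sample per 56-day window. The scheduled exception is j = 8, which holds Week 143 (Day 995) and the Week 145 completion sample (Day 1009). Targets 463 and 995 both select Day 995.

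**6. Study Day.** Applied literally, Section 4.3 gives −1, 0 and 2 for the day before, the day of and the day after first dose. In Appendix 1 every baseline window is either ≤1 or pre-dose, except the 12-lead ECG, where baseline is <1 and the post-infusion ECG sits at Day 1.

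**The case against.** The strongest reply is that these are misprints whose intent is plain, and that little depends on them. Much of this stands.

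- **Primary result.** A reader might infer that the final efficacy time point is wrong. The documents do not support that. Appendix 2 uses baseline and the last ML score above zero with actual dates, and the matched by-visit comparison uses the Appendix 4 days, which are right. On-schedule four-weekly CLN2 records do not change either.
- **ECG baseline.** A reader might infer that a post-infusion ECG coded as Day 0 becomes the QTc baseline. Section 4.4 defines baseline as the last value before study drug, which rules this out. The defect acts through window assignment, not through the closest-record rule, and leaves days after first dose alone.
- **Biomarkers.** A reader might infer that the wrong samples would be analysed throughout. Step 5 shows no change on schedule. Week 151 is not a protocol collection point, and Section 13.3.14 makes the analysis conditional on usable biomarkers being found.
- **The 57%.** It counts offset pairs equally, so it is not a probability, and it needs a visit after Week 145. The protocol's schedule ends there, although treatment lasts at least 144 weeks. The documents do not say how many children were seen later.

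The reply does not remove the conflict for vital signs and CSF surveillance. There the printed rule, followed exactly, reports Week 147 as Week 145 even when both visits are on schedule.

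**Conclusion.** The point holds as a minor correction. Three Appendix 1 targets are wrong on the SAP's own arithmetic: Week 145 by 7 days, Week 151 by 7 days, and the CSF biomarker series by 532 days. The Section 4.3 formula contradicts its own stated result.

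The practical effect is on descriptive by-visit summaries of two-weekly vital signs and CSF surveillance at Week 145: 28 of 49 offset pairs select the later visit, against 0 of 49 with the correct target. This assumes a child with a Week 147 visit, both visits within ±3 days of schedule, and programs that follow Appendix 1 literally. Off-schedule records in other rows could also switch if their days sum to 2019 to 2032. No efficacy conclusion is shown to depend on these errors.

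**What to change.** In SAP Appendix 1, change 1016 to 1009 in every Week 145 row, 15 + j×56 to 547 + j×56, and 1058 to 1051. Leave the window bounds as they are; they already fit the corrected targets. In Section 4.3, add 1 when the visit falls on or after the first-dose date, not only after it. Then confirm that the analysis programs use 1009, 547 + j×56, 1051 and Day 1, and rerun any by-visit table that used the printed values.

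The cost is four text corrections and a program check. Design, data collection and the primary analysis do not change.
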